
Video Coder Training

Each video analysis will be conducted by trained video raters in several passes to determine 1) treatment categories and targets, 2) durations, frequencies, and repetitions, and 3) active ingredients. A minimum of 20% of all the videos will be assessed for interrater reliability ($\geq 90\%$), and minor adjustments to the coding manual may be made. To ensure fidelity, all raters will participate in comprehensive training with a member of our study team and will

be provided with instruction manuals developed for this analysis. Consistent with previous studies, raters will be required to code a mock treatment session using the established framework and reach 90% agreement with the coinvestigator prior to independently coding video data (Lang et al., 2009; Winstein et al., 2003). Videos will be coded and analyzed largely by occupational therapy doctorate (OTD) students in their second or third year of the program, which we previously demonstrated worked well with high interrater reliability (97%) for RTSS treatment groups (Wengerd, 2019).

Statistical Analysis

Data coded using INTERACT will be entered into REDCap and subsequently analyzed using SPSS Statistics. Descriptive statistics will be used to describe the study sample, and all observed treatment categories, treatment sub-categories, treatment targets, and active and material ingredients. Shapiro-Wilk tests will be conducted to assess for normality. Survey results will be reported using descriptive statistics and will be used to inform our video-based observation toolkit development in order to maximize implementation and acceptability of this approach.

Development of a Video Observation Toolkit

The overarching purpose of this Aim 2 is to manualize an approach for video observation to characterize rehabilitation interventions comprehensively using the RTSS framework. This manual will cover the following areas to advance the fields of rehabilitation and implementation science: 1) a comprehensive overview of the pros and cons of video observation compared to traditional implementation science approaches (e.g., chart review, surveys), 2) a step-by-step guide on how to create buy-in with community stakeholders to conduct this kind of work, and how to setup video observation that is unobtrusive to standard care; and 3) a detailed description of how to comprehensively analyzes video observations using the RTSS framework in OT practice settings.

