We will conduct a video-based observational study to assess the practice patterns of OT practitioners working across 3 outpatient settings at OSUWMC. Treatment sessions will be recorded and video data will be analyzed and coded for duration-based and frequency-based events using Mangold INTERACT video coding software. We will use the RTSS framework to guide our analyses, as described briefly in the ‘Guiding Frameworks’ section previously. Examples of the types of interventions we may code and analyze during OT treatment sessions are shown in **Figure 1**.

Our observational study design is appropriate for our descriptive exploratory approach to determine the treatment activities, treatment targets, and active ingredients of OT interventions among OT practitioners and post-stroke patients in outpatient rehabilitation. We previously demonstrated this approach as feasible and wish to expand upon our initial findings to better our understanding of standard care and develop a toolkit which can be used across OT research disciplines for video observation. This methodology will be used to inform a multi-site, nationwide observation study in the future, much like previous groups (Lang et al., 2007, 2009).

Figure 1. Examples of rehabilitation interventions

B. Sample and Recruitment

Participants – OT practitioners

A purposive sample of OT practitioners working in an outpatient rehabilitation at OSUWMC will be recruited for this study. We plan to recruit up to 15 OT practitioners (occupational therapists or occupational therapy assistants) across three different OSUWMC outpatient clinics. OSUWMC employs ~12-15 outpatient OT practitioners who provide services to stroke or SCI survivors on a routine (e.g., monthly) basis. We will record a maximum of 30 sessions per OT participant. We will make our best effort to evenly distribute video recordings across all therapists enrolled, however, this may

vary based on the number of SCI and stroke patients seen by each therapist, number of therapists at each clinic location, etc.

Inclusion Criteria: 1) must be a licensed OT practitioner (occupational therapist or occupational therapy assistant), 2) the OT practitioner must treat at least one adult stroke or spinal cord injury patient with UE sensorimotor impairment per month, 3) the OT practitioner must be willing to be video recorded while treating their enrolled stroke or SCI patients.

Participants – Stroke Patients

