A purposive sample of stroke patients receiving OT at an OSU outpatient rehabilitation clinic will be recruited for this study. We plan to record 90 treatment sessions across three practice settings. To maximize representativeness of our sample, we will not record more than 3 videos per stroke patient participant. As such, we plan to enroll up to 45 stroke patients in this study to allow for potential attrition and/or participants who do not have three sessions left at the time of enrollment.

- Inclusion Criteria: 1) must have a medical diagnosis of ischemic or hemorrhagic stroke, 2) must be \geq 18 years old, 3) must have at least one OT goal related to UE hemiparesis, 4) must have at least one remaining OT treatment session after enrollment, and 5) the patient's OT must be enrolled in the study.

Participants – Spinal Cord Injury Patients

A purposive sample of SCI patients receiving OT at an OSU outpatient rehabilitation clinic will be recruited for this study. We plan to record 60 treatment sessions of SCI patients across three practice settings. To maximize representativeness of our sample, we will not record more than 3 videos per SCI patient participant. As such, we plan to enroll up to 30 SCI patients in this study to allow for potential attrition and/or participants who do not have three sessions left at the time of enrollment.

- Inclusion Criteria: 1) must have a medical diagnosis of cervical spinal cord injury, 2) must be \geq 18 years old, 3) must have at least one OT goal related to UE sensorimotor impairment, 4) must have at least one remaining OT treatment session after enrollment, and 5) the patient's OT must be enrolled in the study.

Recruitment and Retention

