opportunity to learn about the study, receive the informed consent form, and ask questions. For those unable to attend, individual meetings will be arranged to review study details and facilitate the consent process. To protect privacy, all communications will adhere to institutional policies, and personal information will be managed securely. Participants may provide consent during the informational session or in a later, private setting with a study team member. No identifying information will be shared outside the research team. Once enrolled, OT practitioners will be trained on how to recruit patient participants, including sharing study flyers, notifying patients verbally, and providing contact information for the study team. Recruitment materials may also be displayed in public areas of outpatient rehabilitation sites where data collection will occur (e.g., Martha Morehouse, New Albany, Dublin, and Powell). Patient participants will be introduced to the study by their OT. Interested individuals will meet with a study team member in a private or semi-private setting within the clinic to discuss the study procedures and review the informed consent. Formal HIPAA Authorization will be obtained before conducting medical chart reviews. We will also plan to have a member of our study team on site at each location at various times throughout the study, and therapists can make a direct introduction to their potential patient participants in real-time to support recruitment. This approach worked exceptionally well when we collected preliminary data using this approach and we were able to recruit 17 patient participants in under one month. OT participants will be given \$25 per video recording of their sessions, up to \$750 maximum (30 sessions/therapist max.). Payment will be made via a Greenphire ClinCard, a reloadable prepaid debit card, following university policies upon enrollment. Stroke and SCI patients will be given a physical \$25 gift card upon study enrollment for their time and willingness to be video recorded to enhance recruitment and retention efforts.

[figure not shown]

Figure 2. Schematic Diagram of Study Design

confirm eligibility (medical diagnosis and OT goals) and collect pertinent medical information for future analyses, patient participants will be asked to provide their name, date of birth, hand dominance, and impaired UE (right, left, or bilateral) upon enrollment.

C. Detailed Study Procedures

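### Patients enter mainly through the therapist under observation, with no rule on which eligible patients are approached and no count of those who are not

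*Combined protocol and SAP*

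**What the plan says.** The object of measurement is therapist behaviour. Section III.A (Research Design) says the study will "assess the practice patterns of OT practitioners working across 3 outpatient settings at OSUWMC".

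Section III.B (Sample and Recruitment) describes the two patient cohorts in the same way: "A purposive sample of stroke patients receiving OT at an OSU outpatient rehabilitation clinic will be recruited for this study" and "A purposive sample of SCI patients receiving OT at an OSU outpatient rehabilitation clinic will be recruited for this study". Five inclusion criteria follow for each cohort, the last being that the patient's own OT is enrolled. No rule is given for choosing among patients who meet them.

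Under Recruitment and Retention, the same OTs do the recruiting: "Once enrolled, OT practitioners will be trained on how to recruit patient participants, including sharing study flyers, notifying patients verbally". The text adds: "Patient participants will be introduced to the study by their OT". Where a study team member is on site, the first step is still the therapist's: "therapists can make a direct introduction to their potential patient participants in real-time to support recruitment". A second route is optional: "Recruitment materials may also be displayed in public areas of outpatient rehabilitation sites where data collection will occur".

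On representativeness, Section III.B says: "To maximize representativeness of our sample, we will not record more than 3 videos per stroke patient participant". The SCI cohort has the same limit. Video Recording Setup in III.C adds a limit of 30 sessions per OT for the same reason, and the OT sampling paragraph in III.B promises a best-effort even spread of recordings over therapists.

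On counting, Video Coding Analysis in III.D tracks videos per participant and per therapist and videos successfully analysed. It does not mention patients who were eligible, introduced or declined.

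**The concern.** The person whose practice is coded is also the person who usually decides whether a patient hears of the study. Without an approach rule that decision is left to discretion, and without a count no reader can tell how much discretion was used. Later steps do not recover the information: eligibility is confirmed after consent (III.C, Informed Consent and Confirmation of Eligibility), and therapy schedules are requested only after enrolment (III.C, Video Recording Procedures).

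This matters because of the intended use. Section II.A wants the results to define standard care after stroke, and II.B wants them to justify control arms in later trials. Among the coded ingredients are cues, therapist assistance and grading, which plausibly vary with a patient's impairment and engagement. If introduced patients differ from other eligible patients on these, the profile describes the introduced patients. Recording more sessions from patients who enter the same way does not remove the difference. The protocol recognises that filming can alter behaviour, but it deals with this only around the recording itself, not in who is invited.

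**Working it through.** **Step 1: the plan's own figures.** Inputs from III.B: 90 stroke and 60 SCI sessions, at most 3 videos per patient, up to 45 and 30 patients, up to 15 OTs, at most 30 sessions per OT.

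- Stroke: 90 / 3 = 30 patients at minimum; 45 leaves an allowance of 1 − 30/45 = one third, or 90 / 45 = 2.0 videos per patient.
- SCI: 60 / 3 = 20 at minimum; 30 leaves 1 − 20/30 = one third, again 2.0 videos per patient.

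The two targets are consistent with each other. No attrition rate is stated, so they cannot be formally derived.

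**Step 2: what the caps control.** An even split gives (90 + 60) / 15 = 10 sessions per OT. At the cap, 150 / 30 = 5 OTs could supply every session. The caps therefore bound how much one patient or one OT contributes. They place no condition on which of an OT's eligible patients are invited.

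**Step 3: size of a selection error.** Let f be the share of eligible patients introduced, and let m_I and m_N be the percentage frequency of an ingredient in introduced and non-introduced eligible patients. Suppose, for simplicity, that recorded patients represent introduced patients.

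- Frequency in all eligible patients = f × m_I + (1 − f) × m_N
- Reported frequency = m_I
- Error = m_I − [f × m_I + (1 − f) × m_N] = (1 − f) × (m_I − m_N)

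The documents give neither f nor m_I − m_N. Both are assumed below. Errors are in percentage points.

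| Share introduced (f) | Difference 5 | Difference 10 | Difference 20 |
|---|---|---|---|
| 30% | 3.5 | 7 | 14 |
| 50% | 2.5 | 5 | 10 |
| 70% | 1.5 | 3 | 6 |
| 90% | 0.5 | 1 | 2 |
| 100% | 0 | 0 | 0 |

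For example, at f = 50% and a difference of 20 points: (1 − 0.5) × 20 = 10. The number of sessions does not appear in the formula, so a larger sample leaves the error unchanged. An approach-all rule acts on f, and f is what a tally would show.

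**The case against.** The strongest reply is that this is an openly purposive study, described as exploratory and meant to inform a later nationwide one, and that several readings of the text go too far.

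- A reader might infer that OTs are told to pick their patients. They are not. Discretion arises because no rule is set, and flyers in public areas could reach a patient without the OT. That route is optional, so the OT remains the main one.
- A reader might infer that the plan claims a representative sample. It states an aim, tied to the caps. Nor is the patient cap the only measure: there is an OT cap, a best-effort spread over therapists, and a spread over rural, urban and suburban clinics. With about 12 to 15 suitable OTs employed and up to 15 sought, the therapist sample could be near complete. None of this decides which patients enter.
- A reader might infer that every OT would favour the same kind of patient. This is plausible, but nothing in the documents shows it. Payment of $25 per recording, up to $750, gives a reason to introduce many patients.
- The eligible pool may be small relative to the 45 + 30 = 75 patients sought, since an OT need treat only one such patient a month to qualify. The share introduced could then be high and the error small. The documents do not settle this.

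These points limit how strongly the concern can be put. They do not supply an approach rule or a denominator. Calling the sample purposive does not fill the gap either, because no purpose or basis for choosing among eligible patients is stated.

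**Conclusion.** The concern holds as a gap in design and recording, not as a demonstrated bias. Entry runs mainly through the observed therapist, no rule says which eligible patients are approached, and no count would show who was left out, while the results are intended to describe standard care.

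Under assumed differences of 5 to 20 points the error is 2.5 to 10 points with half of eligible patients introduced, 0.5 to 2 points at 90%, and nil at 100%. Its true size and direction are unknown. Larger figures are easy to produce: a 30-point difference at 50% introduced gives (1 − 0.5) × 30 = 15 points. Nothing in the documents supports a difference of that size, so such a figure should not be relied on.

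The change should be made before recruitment starts, because patients who were never introduced cannot be reliably counted afterwards.

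**What to change.** In Section III.B, replace the purposive patient samples with all (consecutive) eligible patients of enrolled OTs, in both cohorts. In the recruitment training that OTs already receive, instruct them to introduce the study to every patient who meets the listed inclusion criteria. Apply the rule within each OT and clinic rather than filling the whole cohort in visit order. Otherwise busy therapists or clinics could dominate, against the plan's own aim of an even spread. The existing caps stay.

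Add an identifier-free tally of patients eligible, introduced, consented and recorded, by OT, clinic and diagnosis, and report it beside the video counts already planned in III.D. State therapist-mediated entry and volunteer consent as remaining limitations.

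The cost is a wording change and a little therapist time; no sample-size figure changes. The tally has limits: it shows the share introduced, not the size of any remaining bias, and it is kept by the OTs themselves.

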All treatment sessions will be video recorded and coded electronically using Mangold INTERACT video analysis software to allow us to analyze both duration (e.g., time spent on active therapy versus rest/setup) and frequency (e.g., number of UE repetitions) data, as well as control for significant participant behavior change (Asan & Montague, 2014). An overview of the video coding framework is presented in **Figure 3**. We will make every attempt to categorize all treatment activities into these categories, though we may find during our analyses that a sub-category needs to be added (e.g., education) and it may be updated through an iterative process. The primary outcomes for this study are the identification of 1) the types of treatment activities (e.g., ‘Organ Function’ versus ‘Skills and Habits’ activities), 2) the targets most often addressed (e.g., increasing strength, improving ability to grasp/release objects, increased independence with dressing, etc.), and 3) the active ingredients of interventions used to treat adult stroke patients with UE hemiparesis.

- Feasibility and Acceptability Surveys

After data collection is complete, we will administer electronic surveys via REDCap to all OT practitioner and patient participants who had at least one OT session recorded to gauge their acceptability and comfort with being video recorded. In addition to study-specific questions about logistics, scheduling, and overall approach,

we will also incorporate well-established implementation science survey metrics to quantify acceptability of this approach (Weiner et al., 2017). Refer to 'OT Practitioner Feasibility Survey' and 'Patient Participant Feasibility Survey' documents for the questions we will ask. Of note, consent to complete this survey will be provided in the paper consent form at the beginning of the study for both video recordings and the survey at the end of their data collection.

Data Management

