categories: 1) Organ Functions, 2) Skills and Habits, or 3) Representations. All observed treatment activities will be categorized into one of the three RTSS categories, and their respective subcategories, or into a fourth category of assessment (not currently existing in the RTSS framework). All seconds of the session will be categorized as ‘active time’ (i.e., activities in each of the four categories), or ‘inactive time’ (i.e., when the patient does not engage in therapeutic activity for greater than 15 seconds consecutively). Treatment Targets: Treatment activities will also be coded with a corresponding treatment target, using a list of 75 potential targets developed through a review of three ICF Core Sets: 1) Rehabilitation Set, 2) Stroke Comprehensive, and 3) Neurological Post-Acute Comprehensive (Bickenbach et al., 2012). To help facilitate the categorization of treatment activities and targets, therapists will be asked to state the primary purpose for each treatment activity during video recording (e.g., “let’s work on stacking cones to increase your shoulder strength”), however clinical reasoning and chart reviews will also be employed to confirm coding accuracy. Active Ingredients: A coding scheme for measuring active ingredients was developed based on previously reported treatment ingredients (Cirstea & Levin, 2007; Gillen, 2015; Host et al., 2014; Stein, 2015; Taub & Uswatte, 2006; Wolf & Nilsen, 2015), discussion with OT practitioners in the field, and clinical experience. Active ingredients will be coded according to this schema as duration-based (time spent using the ingredient), frequency-based (number of occurrences), or both. Activities will be assessed for the following ingredients and coded accordingly: 1) whether feedback was provided, and in what way (e.g., knowledge of performance versus knowledge of results), 2) types of cues provided (e.g., verbal, tactile, etc.), 3) assistance provided by the therapist (e.g., active assisted range of motion) and 4) whether grading/shaping occurred, and in what way. All active ingredients will be coded as ‘present’ or ‘not present’ for each treatment activity. We will also code materials, equipment, and/or modalities used for each treatment activity (e.g., material ingredients). Once all active ingredients are coded with the INTERACT software, we will use the data to systematically describe the activities during treatment sessions using a template recommended by the authors of the RTSS (Tessa Hart et al., 2019). The total number of videos recorded per participant and per therapist will be tracked. This includes videos recorded during each study visit and any additional sessions deemed necessary by the study protocol. The average number of videos recorded per participant and therapist will be reported in the final study analysis to assess consistency in data collection. The number of videos successfully analyzed will be reported, alongside any discrepancies or challenges encountered during the analysis process (e.g., missing data, technical issues). These metrics will be included in the study report to provide transparency in the data collection and analysis process.

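### Does permission to add coding sub-categories during analysis leave earlier videos under an outdated scheme?

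*Combined protocol and SAP*

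**What the plan says.** Section III.C, Video and Photo Data, presents the coding framework and allows for its revision: "we may find during our analyses that a sub-category needs to be added (e.g., education) and it may be updated through an iterative process". The subject of that sentence is the set of treatment-activity categories.

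Section III.D, Video Coding Analysis, sets the coding duty: "All observed treatment activities will be categorized into one of the three RTSS categories, and their respective subcategories", with assessment as a fourth category. Ingredients are handled separately: "Active ingredients will be coded according to this schema as duration-based (time spent using the ingredient), frequency-based (number of occurrences), or both".

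Section III.D, Video Coder Training, describes the reliability check: "A minimum of 20% of all the videos will be assessed for interrater reliability", with a target of at least 90%. The same sentence continues "and minor adjustments to the coding manual may be made" and gives no timing. Raters must first reach 90% agreement on a mock session. Coding is divided by content: "Each video analysis will be conducted by trained video raters in several passes". The earlier feasibility work is cited for "high interrater reliability (97%) for RTSS treatment groups".

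Section III.D, Statistical Analysis, plans descriptive statistics on "all observed treatment categories, treatment sub-categories, treatment targets, and active and material ingredients". Section III.C, Data Management, has the recordings moved to a secure repository.

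**The concern.** The coded frequencies and durations are the study's results. No model or group comparison follows that would reveal a fault in them. If a sub-category were created partway through coding and the earlier videos left alone, one reported percentage would mix two schemes. Activities belonging to the new sub-category would sit under other headings in the early videos, and the new heading would look rarer than it is. If stroke and SCI videos were coded in different proportions before the change, the two aims would be affected unequally, and a difference between cohorts could arise from coding order alone.

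The agreement figure raises a related question. If the double-coded videos were rated before a revision, or were used to make it, the reported agreement would describe a superseded manual. It would not describe the one behind the final data or the published toolkit.

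The protocol contains no sentence that rules either outcome out.

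**Working it through.** The plan gives no figure of its own to reproduce here. The check has a textual part and an arithmetic part.

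**Is there a rule in either direction?** No section requires re-coding, a freeze of the manual or a version log. Equally, no section tells raters to leave earlier videos under an old scheme. Three statements point towards re-coding:
- the updating is described as iterative;
- all observed activities, not only those seen after a change, are to be placed in their sub-categories;
- the videos are stored, so they can be viewed again.

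The instruction manuals mentioned under Video Coder Training are not among the documents, and a re-coding rule would naturally sit there.

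**What is exposed?**
- *Activity sub-categories:* yes, by the explicit permission in Video and Photo Data.
- *Top-level RTSS categories:* only if a new sub-category draws activities across them.
- *The list of 75 targets:* not covered by that permission.
- *Ingredients:* not covered by it either. They are reached only by reading the minor adjustments in Video Coder Training broadly enough to include a new ingredient.

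**Size if nothing were re-coded.** Inputs from section III.B: 90 stroke and 60 SCI sessions, so 90 + 60 = 150. Assumed inputs: p, the true share of activities in the new sub-category, and f, the fraction of videos coded before the change. Also assumed is that p and the number of activities per video are similar early and late. Reported share = p × (1 − f).

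| p | f = 25% | f = 50% | f = 75% |
|---|---|---|---|
| 10% | 7.5% | 5% | 2.5% |
| 20% | 15% | 10% | 5% |
| 40% | 30% | 20% | 10% |

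For a change after 75 videos with p = 20% in both cohorts:
- 60 stroke and 15 SCI coded first: stroke 0.20 × (1 − 60/90) = 6.7%; SCI 0.20 × (1 − 15/60) = 15%.
- 45 and 30 coded first: 10% in both.
- 30 and 45 coded first: stroke 0.20 × (1 − 30/90) = 13.3%; SCI 0.20 × (1 − 45/60) = 5%.

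**Size if earlier videos are re-coded.** The effective f is 0, so the reported share is p × (1 − 0) = p in every row and in both cohorts.

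**Are the large cells plausible?** Take p = 20% and f = 50%, count only one activity per video, and assume independence. The chance that the missing sub-category never occurs in the early videos is 0.8^45 ≈ 0.00004 for stroke and 0.8^30 ≈ 0.001 for SCI. Occurrence is not the same as recognition, and sessions cluster within patients and therapists, so these are rough guides. Still, a common gap would probably be noticed early, when f is small. A gap that stays hidden for long is probably rare, so p is small.

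**Agreement sample.** 20% of 150 is 30 videos. If these were spread evenly over coding and one change came at f = 25%, 50% or 75%, then 30 × (1 − f) = 22.5, 15 or 7.5 of them would be rated under the final manual. If they were the first 30 coded, none would be, for any change after video 30. This bears only on the codes that changed.

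**The case for a change.** The best case for a change is that nothing in the text actually closes the gap. The several passes divide the work by content and are not repeat coding. The mock session comes before independent coding, so it cannot cover later revisions. The promise to report discrepancies gives missing data and technical issues as its examples. The 30-video feasibility study is presented as stroke work, and its 97% agreement is for RTSS treatment groups, so neither shows that sub-categories are settled for SCI. The protocol's own example, education, might even move time between active and inactive. A few sentences would settle the matter.

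Most of this is accurate, and two points stand: the protocol does not state a re-coding rule, and it does not say which manual version the agreement figure refers to. Three things weaken the case for acting on them. First, the harm requires raters to create a sub-category and then not apply it to stored videos, contrary to the duty to categorize all observed activities. Second, the permissions are conditional: the text says changes may be found necessary or may be made, not that they are expected, and those to the manual are limited to minor ones. Third, dividing the passes by content means that re-coding can be confined to the affected codes, so the sensible course is also an affordable one. Excluding and replacing videos used to adjust the manual, or fixing a stroke and SCI split of the agreement sample, would go beyond the gap and is partly preference.

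**Conclusion.** The concern does not call for a change. The protocol leaves a coding practice unwritten, but its own terms lead competent coders to apply an added sub-category to the videos already coded. On that footing the distortion is zero. The figures for the opposite case, such as 20% reported as 10%, depend on assumed values of p and f and on no re-coding at all. The true size is unknown, and is nil if no code is added.

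Any exposure lies mainly in the sub-category breakdown of a descriptive, exploratory study. An oversight could be put right from the stored recordings before reporting. Which manual version the agreement figure reflects can be stated in the study report, alongside the analysis challenges that section III.D already commits to describing.

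This conclusion assumes that the recordings remain available through analysis and that the unseen coding manual does not direct raters to leave earlier videos as they were.
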